Prior to fMRI runs, subjects practiced meditating at home in a supine position (in contrast to normal upright sitting position) with a audio recording of fMRI noise. Subjects came to the M.U.M. lab and did a 'dry'

run in a fMRI machine mockup with audiotape to simulate the actual run experience (noise, claustrophobia, etc.). Physiological markers were recorded and the signaling paradigm between the subject and the experimenter was tested (use of audio vs. light beam signals). Subjects filled out consent forms at M.U.M. and UI before testing. Following selection procedures, subjects went to the UI MR Center for testing.

C.2.3. Acquisition Protocol.

Subjects were reminded again of the nature of the experiment and signaling protocols. Following setup and positioning in the scanner, we acquired standard anatomic scans lasting about 40 minutes before experimental scans. The anatomic scans included: (1) a T2-weighted sagittal localizer using a fast spin echo sequence (TE/TR 100/4500; 24 5mm slices; 2mm space; 256X224, NEX2 1:30); and (2) a volumetric scan (3D RF-spoiled gradient echo sequence with TE/TR 7/26 ms; 256X192 matrix). Experimental scans included (1) a 2D T1-weighted scan of the slices to be acquired in the fMRI study (2D RF-spoiled gradient echo sequence with TE/TR 7/26ms), and (2) an 8-shot EPI sequence of the slices to be acquired (TE/TR 40/3000 ms). The 8-shot EPI sequence and T1-weighted slices are used to align the fMRI data with the volume scan. For fMRI studies, we used the EPI sequence with 128 by 128 data acquisition matrix, TE of 40 msec, TR of 3 sec, FOV 24 cm, slice thickness of 5 mm. Since fMRI was conducted on a single slab (software limitation of the 1.5T GE scanner system), we initially chose a slab (5 slices, 118 degree angle) that traversed regions of greatest interest (see figure 1A): progressing from anterior/superior to posterior/inferior, the regions of interest included the prefrontal cortex (anterior polar, dorsolateral, ventromedial and rostral anterior cingulate), the basal forebrain and hypothalamus, the thalamus, the mesencephalic brainstem and the cerebellum. We were aware of the possibility of tissue ghosting.

[figure not shown]

Figure 1. fMRI of TM Cycling Run: An AFNI analysis of a 5-min TM-cycling task comprising alternating 45-sec epochs of TM practice and comparison task (eyes-closed mental counting by 2's). (A) The location and orientation of a brain slice. (B) The fMRI scan of this slice with the correlational analysis superimposed as colored pixels (correlation threshold = 0.45). A number of regions distributed across the brain slice display pixels indicating increased (blue) or decreased (orange) signal intensity. (C) Graph plotting the signal intensity over the 5-min cycling run for the pixel located in the basal forebrain noted by the arrow (TM, meditation epoch; CT, control task epoch). This picture is meant to convey the functionality of our acquisition and analysis system. Since the data is from only a single run one cannot draw any specific significant conclusion regarding neural change associated with the cycling. In addition, this subject has considerable artifact (grey areas signify signal dropout) often seen in ventral slices due to dental work and/or air-bone interfaces. (Color copies in Appendix; R21, *fMRI Study of Brain Mechanisms during Meditation*).

Constructed a map of the correlation of the task-reference function with the corrected fMRI images. The task-reference function is created by convolving a standard hemodynamic response function—a gamma variate function with parameters described by Cohen [170] on the time series of the boxcar design of 0's and 1's. The results are displayed based upon a chosen level of significance, as either response time series maps for scans across each epoch and the entire run, and anatomic image overlaid with pixels possessing significant (positive or negative denoted by color) correlation. Data from the few noncycling runs were analyzed but did not have sufficient SBQ periods to yield reliable comparisons. One subject had very few (and very short) SBQs and the other subject had very few SBQs. The noncycling runs were conducted last in the early protocol and after a considerable period of lying in the scanner. Subject selection in this application will maximize for the number of individuals with SBQs in both cycling and noncycling runs.

C.2.6. Results of Cycling Runs.

C.2.6.1 Successful Practice of Meditation: The study clearly demonstrated that subjects were able to meditate during the fMRI recording as indicated by self-reports of the normal range of meditation experiences, and the presence of multiple spontaneous breath-quiescent periods, indicative of the reoccurrence of both substates during TM practice: the process of de-excitation and the most de-excited substate corresponding to SBQ.

C.2.6.2 System Functionality: The study demonstrates the collaborative effort could yield images of task-dependent significant BOLD intensity changes. Serving as a positive control for the functionality of the overall system, the motor task revealed increased signal intensity localized over the motor cortex representation of the hand (data not shown). Significant pixels appear with little background noise within a few cycles. By the end of the motor run, a clear overlay of the cortical area was evident, as expected.

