B.2.4.2. Experimental verification of de-excitation substate. In Section D.5.1, we designed an experiment to "frame" the de-excitation process. The entire de-excitation process begins from the ordinary thinking level. With the start of the mantra or sound, thinking settles down and process ends with the distinct inner subjective experience of awareness without thoughts, correlated with SBQ. Preliminary research indicates that long, 60 second cycling protocols will include the entire de-excitation substate, ending with a SBQ [[name] and [name], unpublished research, 2001][9]. In the subject screening process, this long cycle time run will provide an initial estimate of the average time of transit for each subject terminated by SBQ. With this information, we can more accurately "frame" the de-excitation substate for each subject using shorter (20-40 sec) cycle periods. This will permit imaging of the de-excitation substate alone, without contamination with SBQ and any subsequent brain substates.

B.2.4.3. Summary of substate strategy. Progress in understanding brain dynamics of meditation and other CAM techniques will depend at least partially upon the elucidation of the temporal structure of physiological and psychological events during the practice [see, 65]. Previous EEG and autonomic research has begun to delineate distinct substates during TM practice [8-10, 22, 67, 69]. It is unlikely these substates are 'epi-phenomena,' but rather, are reproducible, essential brain states that comprise the practice of the TM technique. With the exception of TM and one other very rudimentary meditation model [see references in 65, 73], all meditation techniques lack an empirically defined temporal structure. This may be a considerable hindrance to progress in CAM research, as well as the clinical application and interpretation of meditation techniques. In this context, formulating a neural model of substates during TM practice could be the basis of understanding: (1) the immediate and long-term effects of TM practice, (2) how TM practice can benefit specific clinical groups, and (3) whether similar substates are found in other meditation techniques.

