The screening of 15 subjects will involve minimal recording time and analysis time. The recording time will be just over 1.5 hr for tests (a 5-min motor task cycling-run, TM cycling-runs, and uninterrupted self-paced TM runs) and 40 min for standard anatomic scans. The analysis will determine whether (1) the subject was able to meditate in the magnet as evidenced by breath changes and subjective reports, and (2) the fMRI images are relatively free of physiological and movement artifacts.

D.4. Population Selection.

The communities of Fairfield, IA and Greater Detroit, MI are uniquely suited for this study, with over 3,000 individuals who have been practicing the TM technique from a few months to over 30 years (average 10-20 years). This group ranges in age from 10 to over 80 years. We will attract 100 candidate subjects by email list and advertisement in Fairfield and Detroit. We will *pre-screen* potential subjects in Fairfield and Detroit, and then *screen* subjects with a trial run in the magnet in the HFH Neurology NMR Facility. Subjects will be reimbursed for participating in any of the five experiments detailed below.

D.4.1. Prescreening of subjects.

We will identify 30 subjects from the 100 candidates through the prescreening process, preferably from the Greater Detroit area (60 min driving distance). During pre-screening, subjects will learn about the nature of fMRI recording, the research design, and the inclusion/exclusion criteria. The criteria will be based on factors that may possibly affect measurement of BOLD activity:

- (1) **Basic demographics:** (a) Age 20 to 55 years; (b) All right-handed (Edinburgh test of handedness); (c) English speaking; (d) No alcohol or cigarette use, and; (e) Similar number of men and women.
- (2) **Physiological:** (a) No serious medical conditions; (b) No prescription medication; (c) No learning disabilities; (d) No history of head trauma; and (e) No metal within or on the body (including extensive dental work).
- (3) **Time:** Subjects should be able to participate in the two experiments.
- (4) **Scanner:** No claustrophobia and ability to meditate comfortably
- (5) **SBQ:** Subjects should display SBQ at a rate of 10 per 20min of noncycling meditation.

D.4.2. Screening of subjects.

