We estimate 30 subjects will meet the first three criteria. We will then assess medical history and obtain written consent (see Section E). They will be given an audio tape and instructed to practice the TM technique at home with earplugs, lying down in a darkened room, with the audiotape playing the fMRI machine noise. This home practice will accustom subjects to the fMRI experimental conditions. Then, subjects will come to either the HFH or M.U.M. laboratory for a trial run in a cardboard mockup of the MRI

machine with the same audiotape. In the mockup, subjects will practice TM, train with the signaling protocol, with both control conditions (passive listening and mental-counting), and have respiratory and autonomic data acquired, to satisfy the fourth criteria above. Subjects will pass this last two pre-screening criteria, if they are comfortable with the environment and protocol, and demonstrate clear periods of spontaneous breath-quiescence during the trial run. We estimate 20 subjects will qualify for MR imaging.

Of the 20 candidates, we expect about 5 individuals will not meet the final two criteria necessary for inclusion in the study during the first MRI scan at HFH. These two criteria are:

- (6) **MR protocol criteria:** (a) No claustrophobia; (b) No metal placements within or on the body (including extensive dental work); (c) Minimal recording artifacts (e.g., low levels of head movement and tissue inhomogeneity, due to sinus configuration and dental work).
- (7) **Meditation criterion:** Appropriate meditation experience based on subjective reports and respiratory patterns during TM practice in the MRI environment.

We expect that a minimum of 15 subjects will meet the full set of screening criteria and will be the subject pool for the five experiments in this grant. One of the advantages of running the same subjects multiple times is that within- and between-subject variance can be assessed.

D.4.3. Estimation of Sample Size.

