We determined sample size of 10 subjects based on published neuroimaging studies [111, 186]. The fMRI meditation study of Lazar et.al. [143] reported significant results with five subjects. Two PET studies of meditation [142, 144] reported significant signal changes with nine and four subjects, respectively. Litscher's recent study of Qigong [187] examined cerebral blood flow using two subjects, but reported no estimates of significance. Newberg et.al. [73] neural SPECT study of Tibetan meditation reported significant blood flow changes with eight subjects. An examination of 50 reports on PET or fMRI imaging of hypnosis, acupuncture, complex cognitive tasks, or simple sensory and motor stimulation showed that statistical significance was found with 10 or less subjects [see for example, 108, 111, 162, 188, 189-199].

D.5. Examine the Patterns of Neural Activity during the De-Excitation Substate (Aim 1).

Experiment 1: Selection of epoch length and control condition to image the de-excitation process.

D.5.1. Hypotheses. We will be testing two hypotheses in this experiment.**D.5.1.1 Epoch length.** We hypothesize that the shorter epoch length in a ABC-cycling protocol (randomly-ordered meditation and controls) will best 'frame' the initial de-excitation process due to significantly higher signal-to-noise ratio, higher signal intensity and less variance in the statistical test;

D.5.1.2. Control conditions. We hypothesize significant differences in signal intensity across the three different epoch conditions—TM, passive-attending and mental-counting, including in rank order: de-excitation will be maximum for TM, then passive-attending, and lastly, mental-counting.

D.5.2. Issues.

D.5.2.1. Epoch length. Epoch length will be pre-framed during our subject selection protocol. We will examine two epoch lengths centered on this preliminary value. The best frame will include maximum duration of the de-excitation process without the actual onset of a SBQ for most of the meditation epochs.

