We will record fMRI (in first 10 subjects meeting inclusion criteria) during randomly ordered epochs of controls and TM practice. We will use two cycling ABC-run with eyes-closed. Each ABC-run comprises TM and two control conditions: (1) listening passively to nature (ie, ocean) sounds or (2) mental-counting by '2s'. An ABC-run (for example, using 30 sec epochs) will last about 22min, including 45 total epochs, 15 epochs each condition. This will result in 22 min/run x two epoch lengths = 45 min of testing, plus 40 min of preliminary anatomic scans, for a total time of less than 2 hr per MRI session. Whole-brain scans will be recorded from 19 slices per scan. At the end of each 22-min run, subjects will be asked to report their experiences. Carryover effects will be minimized by: (1) inserting one minutes breaks between runs. During these breaks we will be speaking and de-briefing the subjects; and (2) randomly presented control conditions in the same run. With this design, *within*-sets comparison will provide an estimate of the *minimal* carryover effects and *across*-sets will provide an estimate of *maximal* carryover effects.

D.5.4. Analysis for Hypotheses 1 & 2.

The data will be processed, and clusters of significant fluctuations in signal intensity will be noted (see Sect. D.2.2-D.2.3.). We expect clusters of fluctuations in signal intensity in 4-8 brain areas (see Sect. B.). The Z-statistics for areas of significant fluctuations in signal intensity will be noted from all runs and used as the variate in a repeated measures MANOVA. In this MANOVA, brain areas (4-8 estimate), and epoch condition (3) will be the factors, and the epoch-lengths (2) will be the repeated measure. For all main effects, individual comparisons will be conducted.

1. We expect **main effects for brain areas**, indicating significant differences in signal intensity between one or more brain areas. These changes may include in rank order: basal forebrain increases, slight cerebral and cerebellar cortex and mesencephalic reticular formation decreases, and no decreases in medial thalamus.
2. We expect **main effects for epoch condition**, indicating significant differences in signal intensity across the three different conditions—TM, passive-attending and mental-counting. These changes may include in rank order: de-excitation will be maximum for TM, then passive-attending, and lastly, mental-counting.

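### Experiment 1 scores every TM epoch wholly as TM, so scans from epochs that run into SBQ enter the Aim 1 de-excitation estimate, and more so at the longer epoch length

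*Protocol*

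**What the plan says.** All references are to the Protocol.

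- **Goal of Aim 1 (B.2.4.2).** Individually framed epochs of 20 to 40 s are to isolate one substate: "This will permit imaging of the de-excitation substate alone, without contamination with SBQ and any subsequent brain substates".
- **How the frame is set (B.2.4.2).** A 60 s cycling run at screening is expected to end in SBQ, and "this long cycle time run will provide an initial estimate of the average time of transit for each subject terminated by SBQ".
- **Lengths tested (D.5.2.1).** "We will examine two epoch lengths centered on this preliminary value". The best frame is the longest stretch of de-excitation "without the actual onset of a SBQ for most of the meditation epochs".
- **Run layout (D.5.3).** With 30 s epochs, a run "will last about 22min, including 45 total epochs, 15 epochs each condition".
- **Analysis (D.5.4).** Z-statistics from significant clusters go into a repeated-measures MANOVA. Brain area and epoch condition (three levels: TM and two controls) are the factors, and epoch length (two levels) is the repeated measure. TM is one undivided level.
- **Covariables (D.2.2).** Respiration, pulse oximetry and electrocardiogram are recorded in step with the images, and the physiological series enter the voxel regression.
- **Selection on SBQ.** Criterion (5) in D.4.1 reads "Subjects should display SBQ at a rate of 10 per 20min of noncycling meditation". In the mock-up (D.4.2) subjects must "demonstrate clear periods of spontaneous breath-quiescence during the trial run", with no run type named. The pilot text just before C.2.6 says "Subject selection in this application will maximize for the number of individuals with SBQs in both cycling and noncycling runs". One subject pool serves both experiments.

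**The concern.** The stated goal and the stated analysis do not match. The goal is a substate with no SBQ in it. The frame tolerates SBQ onset in a minority of epochs, and once an onset occurs nothing in D.5.4 separates what follows from what came before. A TM epoch that is half de-excitation and half SBQ counts as TM throughout.

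Two results are exposed. The first is the condition contrast (Hypothesis 2): the TM coefficient becomes a blend of the Aim 1 and Aim 2 substates, and it takes in scans with altered breathing although D.1 says Aim 1 should be free of the respiratory confound. The second is the epoch-length comparison (Hypothesis 1): the longer epoch gives more time for an SBQ to begin, so a difference between lengths partly reflects how much SBQ each one contains.

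The protocol knows this problem. C.2.6.3 reports that substate mixing in the pilot cycling run was uncontrolled, and that the displayed clusters therefore need not represent de-excitation alone.

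**Working it through.** **1. The plan's own figures.** D.6.3 expects 3–5 SBQ per 5 min of meditation. Over four periods that is 4 × 3 = 12 to 4 × 5 = 20, the range stated in D.6.4. The example ABC run is 45 × 30 s = 1,350 s = 22.5 min, which agrees with about 22 min. TM time per run is 15 × 30 s = 7.5 min.

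**2. SBQ rates, all from noncycling meditation.**
- D.4.1 criterion (5): 10 per 20 min = 0.5 per min.
- D.6.3: 3–5 per 5 min = 0.6–1.0 per min.
- D.6.4: 25–30 per 30 min = 0.83–1.0 per min.

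**3. Chance that a TM epoch contains an SBQ onset.** Assume a constant onset rate r that carries over unchanged to cycling. For an epoch of L seconds, P = 1 − exp(−r × L/60).

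| r per min | 20 s | 30 s | 40 s | 60 s |
|---|---|---|---|---|
| 0.5 | 15% | 22% | 28% | 39% |
| 0.6 | 18% | 26% | 33% | 45% |
| 0.83 | 24% | 34% | 43% | 57% |
| 1.0 | 28% | 39% | 49% | 63% |

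At 30 s this is 15 × 0.22 = 3.3 to 15 × 0.39 = 5.9 of the 15 TM epochs in a run.

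**4. Share of TM time after the first onset.** Under the same assumptions, with x = r × L/60, the mean share of an epoch from first onset to its end is 1 − (1 − exp(−x))/x.
- 20 s: x = 0.167 to 0.333, share 8% to 15%.
- 30 s: x = 0.25 to 0.50, share 1 − 0.2212/0.25 = 12% to 1 − 0.3935/0.50 = 21%.
- 40 s: x = 0.333 to 0.667, share 15% to 27%.

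D.1 gives SBQ a typical duration of 10–40 s, so an SBQ that begins inside such an epoch will often last to its end.

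**5. A model closer to the protocol's own picture.** B.2.4.2 describes SBQ as the end point of a transit with an average duration. Suppose that time is normal with mean 30 s and a coefficient of variation of 0.2–0.5 (both assumed). The chance of onset is then 5–25% within 20 s, 50% within 30 s and 75–95% within 40 s. If the value on which the two lengths are centred is the average transit time, the longer length exceeds it, and under any symmetric spread more than half of its TM epochs contain an onset. If the centring value is set below the transit time, the share is smaller.

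**6. What the models agree on.** The share is not zero, and it rises with epoch length. The constant-rate figures stay below 50%, so they are compatible with the target in D.5.2.1. They are not compatible with SBQ-free imaging as promised in B.2.4.2.

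**The case against.** A reader might infer something stronger: that the pilot-section sentence makes SBQ in cycling runs a recruitment goal, and so selects for the very mixing Experiment 1 must avoid. The text does not support this. The sentence maximises the number of individuals who show SBQ, not SBQ per short epoch. The operative criterion (5) counts noncycling SBQ only, and no listed criterion selects on SBQ in the 20–40 s runs. B.2.4.2 also gives a proper use for SBQ in a cycling run: without it, the 60 s screening run cannot yield a transit time. Deleting the reference to cycling could remove that calibration, and it would change none of the percentages above, which come from noncycling rates.

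Other points against:

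- **The figures are rough.** Constant onset runs against a picture in which de-excitation comes first, and rates from uninterrupted meditation may not hold when meditation is interrupted every 20–40 s. This stands, and the figures are illustrative only.
- **Comparing two lengths is itself the test for mixing.** D.5.4 item 3 says longer epochs may bring in new processes. This is partly right, and the unseparated comparison should therefore be kept alongside the separated one. It does not clean the TM estimate at either length.
- **Respiration is already a covariable.** It can absorb signal that follows breathing, but it does not identify a different neural substate. D.6.2.1 also has the CO₂ monitor bought in Year 2, whereas D.3 places Aim 1 in Year 1.
- **The pilot should not be over-read.** C.2.6.3 gives five reasons not to extrapolate, of which mixing is one, and says fairly robust changes persisted despite it. Mixing alone cannot be said to have spoiled the pilot map.
- **An analysis plan may cover epoch scoring.** It may, and it is not at hand. But D.5.4 already fixes the variate, factors and repeated measure, and as fixed they leave SBQ scans inside TM.

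**Conclusion.** The point holds as a mismatch between what Aim 1 promises and what D.5.2.1 and D.5.4 deliver. SBQ scans are admitted in a minority of TM epochs, are analysed as de-excitation, and become more frequent as epochs lengthen. The plausible size, about 15–28%, 22–39% and 28–49% of TM epochs at 20, 30 and 40 s, rests on a constant onset rate and on noncycling rates applying to cycling, so it indicates order of magnitude and probably overstates early onsets. If the two lengths straddle the average transit time, the longer one could fare worse. The direction of the effect on any brain area is not known from the document.

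The exposure comes from serving both aims with one pool of frequent-SBQ subjects, which Experiment 2 needs. The difference between the pilot-section sentence and criterion (5) is a minor matter of wording.

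**What to change.** 1. **Separate the scans.** In the D.2.2/D.5.4 regression, mark SBQ onset from the respiration channel and enter scans from that onset to the end of the same TM epoch as their own regressor. The TM coefficient used in the condition contrast then rests on SBQ-free scans.
2. **Report exposure.** Give the share of TM epochs with an SBQ onset for each epoch length.
3. **Show the epoch-length comparison both ways,** with and without the separation, since SBQ contamination is part of what it is meant to reveal.
4. **Reconcile the wording.** Keep the reference to cycling in the pilot-section sentence, but state that SBQ in cycling is sought only in the 60 s screening run used to estimate transit time, so that it agrees with criterion (5) in D.4.1.

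Cost: a few sentences and one regressor, with no extra scanning. The TM coefficient loses some scans, roughly 8–27% of TM time under the constant-rate assumption and probably fewer if early onsets are rarer. The new regressor will be correlated with the respiration covariable, but it is a nuisance term whose own coefficient need not be interpreted.
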